### Cohort Sampling

This is a retrospective cohort study with risk-set sampling for exposure status of convalescent plasma using EHRs in the Baylor Scott & White Health (BSWH) healthcare delivery system. In brief, patients who received convalescent plasma will be matched to a similar population who did not receive convalescent plasma around the same time ( $\pm 2$  days) of transfusion across sites. The administration date of convalescent plasma for the treated population and the matched date for the untreated population are thereafter referred as the index date. The matching scheme for risk-set sampling is defined in step-by-

step points in the following paragraph. The follow-up for the matched cohort will start from the index date and continue until the end of the observation period. The observation period for this study is defined as at least 28 days from the index date. In other words, the index date must be at least 28 days prior to the date of data pull to allow for adequate follow-up and minimize selection bias from informative censoring due to death or discharge for palliative care. An unexposed patient at the index date could receive convalescent plasma during the follow-up and the follow-up will be censored at the administration date of convalescent plasma (Figure 1).

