The propensity score is defined as the probability of a patient receiving convalescent plasma conditioned on their observed baseline covariates. Baseline is defined as the period prior to and including the index date. Baseline covariates for the propensity score modeling is listed below and further defined in Appendix 2. To account for confounding by baseline covariates described below, a logistic regression will be fitted to estimate the probability of receiving convalescent plasma. In the event of low frequency of certain covariates, that may cause model convergence problem, such covariates will be removed from the propensity score model. Covariates that are strongly related to convalescent plasma transfusion but only weakly related to the primary outcome will not be included in the propensity model to preserve precision of the estimates. Exposed and unexposed patients will be matched according to propensity score with nearest neighbor caliper matching algorithm without replacement with a match ratio up to 1:4 based on the power calculation (Section V. Sample Size). Propensity density plots pre- and post-matching will be evaluated for overlapping areas.

- Age (continuous)
- Race and ethnicity
- Hospital site
- Comorbidities
- Concomitant medications
- Oxygen requirements as a proxy for disease severity (Appendix 3) 4-12 hours prior to the index date

- Laboratory results: creatinine, D-dimer, troponin, absolute lymphocyte count, ferritin, C-reactive protein
- Vital signs: Respiratory rate (min), Heart rate (min), Systolic BP (mmHg), Temperature (°C)

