### **Covariates**

Covariates including those for risk-set sampling and propensity score matching (See Cohort Sampling) will be assessed during baseline and are listed in Appendix 2. Baseline is defined as the period prior to and including the index date. For variables (e.g., vital signs and comedications) assessed at multiple time points, the value closest to the index date will be used. However, for oxygenation, the worst measures 4-12 hours prior to the index date will be used. For variables (e.g., cardiovascular conditions) that are usually collected at hospital admission or possibly in previous healthcare encounters for other health concerns, the value will be searched in the past year from and including the hospital admission date, unless specified otherwise. The lookback period for each covariate is listed in Appendix 2.

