## Appendix 2. Baseline covariates

- Age (continuous)
- Race and ethnicity
- Site
- Comorbidities in the past 12 months including the index date unless specified
  - History of cancer
    - Hematopoietic
    - Solid tumor excluding non-melanoma skin cancer
    - Non-melanoma skin cancer
  - Cardiovascular conditions
    - Stroke
    - Thrombotic or thromboembolic complications including stroke, myocardial infarction, venous thromboembolism, deep vein thrombosis, and pulmonary embolism
    - Hypertension
    - Heart failure
    - Cardiac arrhythmias including ventricular tachycardia, ventricular fibrillation, atrial arrhythmia, and cardiac arrest
  - Chronic respiratory disease
    - Chronic obstructive pulmonary disease
    - Asthma
  - Diabetes
  - Chronic kidney disease 1-4
  - Chronic kidney disease 5 or end-stage renal disease
  - Chronic liver disease
  - History of organ transplantation
  - HIV
  
  - Obesity at admission
  - Sickle cell disease
- Pregnancy status (yes, no) from index date to study completion
- Comedications from hospital admission to the index date
  - Antiviral drugs
    - Remdesivir
    - Lopinavir/Ritonavir
    - Other HIV protease inhibitors.
  - Hydroxychloroquine/Chloroquine
  - Azithromycin
  - Glucocorticoid/Steroids
    - Dexamethasone
    - Prednisone
    - Hydrocortisone
    - Methylprednisolone
  - Anti-platelet agents
  - IL-6 inhibitor/antagonist
    - Tocilizumab
    - Sarilumab

- Siltuximab
  - ACE-Inhibitors (ACEi)/Angiotensin Receptor Blockers (ARBs)
  - Anti-thrombotic drugs
- Disease severity based on level of oxygenation support (Appendix 3) 4-12 hours prior to index
- Vital signs closest to the index date
  - Respiratory rate
  - Heart rate
  - Systolic blood pressure
  - Temperature
- Laboratory results closest to index date
  - Creatinine,
  - D-dimer
  - Cardiac troponin (TnI or TnT)
  - Absolute lymphocyte count
  - Ferritin
  - C-reactive protein

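### Pregnancy, listed as a baseline covariate, is dated from the index date forward, and same-day vitals, laboratory values and diagnoses are not limited to the time before transfusion

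*Protocol*

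**What the plan says.** The Covariates section of the Protocol states: "Baseline is defined as the period prior to and including the index date". Step 4 of Cohort Sampling gives the same definition. The Covariates section adds that the covariates "will be assessed during baseline and are listed in Appendix 2". Step 4 ties that appendix to the model: "Baseline covariates for the propensity score modeling is listed below and further defined in Appendix 2".

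Appendix 2 then sets these windows:

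- Pregnancy: "Pregnancy status (yes, no) from index date to study completion".
- Comorbidities: "Comorbidities in the past 12 months including the index date unless specified". The list includes a thrombotic and thromboembolic composite and a cardiac arrhythmia composite that covers cardiac arrest.
- Vital signs: "Vital signs closest to the index date". Laboratory results follow the same rule.
- Oxygen support: a window of 4 to 12 hours before index.

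The index is a calendar date: "The administration date of convalescent plasma for the treated population and the matched date for the untreated population are thereafter referred as the index date". Follow-up starts from that date. Step 2 of Cohort Sampling says that linkage to the administration record will give both the date and the time of transfusion.

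**The concern.** A propensity score should use only what was known before treatment. Two things in Appendix 2 depart from that.

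First, the pregnancy window starts where baseline ends. The chance of a pregnancy being recorded then depends on how long the patient survives and stays under observation, which is tied to the primary outcome of 28-day in-hospital mortality. Read literally, a pregnancy documented only before the index date does not count.

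Second, the index day belongs to both baseline and follow-up. A temperature, respiratory rate or heart rate taken after the transfusion on that day qualifies as baseline, although the listed safety outcomes include febrile reaction, circulatory overload and acute lung injury. A thrombotic event or arrhythmia diagnosed after transfusion on that day also qualifies as a prior comorbidity. Unexposed patients have a matched date but no transfusion, so any such contamination differs between the groups. Adjusting for a consequence of treatment can remove part of its effect or introduce selection bias.

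**Working it through.** The Protocol gives no figure to reproduce on this point. The check compares the windows and does some date arithmetic.

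**1. Length of the pregnancy window.** The Protocol does not define study completion. Assume it is the study period end, October 25, 2020 (Study Period).

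- Index July 1: 30 (rest of July) + 31 + 30 + 25 = 116 days after index.
- Index September 27, the last administration date in Study Period: 3 + 25 = 28 days.
- Index September 28, the last date in step 1 of Cohort Sampling: 2 + 25 = 27 days.

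Counting the index date itself, the window spans 29 calendar days (September 27) to 117 (July 1). Only one of those days, the index date, lies within baseline. The window covers essentially the whole 28-day outcome period and is about four times as long for the earliest patients as for the latest (116 / 28 = 4.1).

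**2. Index-day values.**

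| Covariate | Window in Appendix 2 | Post-transfusion value on the index day excluded? |
|---|---|---|
| Oxygen support | 4 to 12 hours before index | Yes |
| Vital signs | nearest to the index date | No |
| Laboratory results | nearest to the index date | No |
| Comorbidities | 12 months, index date included | No |
| Comedications | admission to the index date | No |

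The Covariates section confines all of these to baseline, which rules out values from later days. It does not rule out later hours of the index day. Only oxygen support has an explicit limit before index. A window counted in hours needs an index clock time, so the Protocol already needs one for both groups.

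**3. Double counting.** The thrombotic and arrhythmia composites in Appendix 2 list the same components as the two composite safety outcomes in Study Outcomes. Appendix 2 includes the index date, and follow-up starts on it. One event on that day can therefore satisfy both definitions.

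**4. Route to the primary result.** Comorbidities, comedications, vital signs and laboratory results are named in the propensity-score list of step 4. Pregnancy is not; it could enter only through the reference to Appendix 2. Comparative Analyses then adds to the Cox model any covariate whose absolute standardized difference exceeds 0.1 after matching. Values altered by transfusion could thus affect the matching, the outcome model or both.

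**The case against.** The strongest reply is that little is at stake. Pregnancy is not in the step 4 list, and step 4 removes low-frequency covariates that may cause convergence problems. A pregnancy recorded soon after index would nearly always have existed at index. For vitals and laboratory values, the wording is loose rather than contradictory and concerns only part of one calendar day. The main severity measure, oxygen support, is protected. Appendix 4 reserves a column for the time point of each data element, where a clock-time rule could be written. All of this stands as a limit on size. It does not remove the pregnancy contradiction, and Appendix 4 is still blank, so at present nothing excludes values taken after transfusion.

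A reader might also infer that the two comorbidity windows conflict, because the Covariates section says "the value will be searched in the past year from and including the hospital admission date" while Appendix 2 runs to the index date. They do not conflict. That sentence goes on to allow exceptions specified elsewhere, and the next one refers lookback periods to Appendix 2, so the appendix governs. Nor should comorbidities stop at admission. The Exposure section allows plasma at any time in the stay, and Secondary Analyses plans a stratum of 72 hours or more from admission. Events between admission and transfusion are pre-treatment confounders and should be kept.

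It is tempting to say that about half of the index-day readings follow transfusion. That needs evenly spread transfusion times and regular readings, neither of which is in the Protocol. A later reading is also not necessarily one changed by transfusion.

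**Conclusion.** The pregnancy entry contradicts the Protocol's own definition of baseline and should be corrected. Its numerical effect is probably small, on the assumptions that pregnancy is uncommon in this cohort (no figure is given) and was usually already present at index. It does not follow that every pregnancy is misclassified.

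The index-day problem is a permissive definition, not a contradiction. It reaches covariates that are certainly candidates for the propensity score. The number of patients affected, and the size and direction of any bias in the hazard ratio, cannot be derived from the Protocol.

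A reader might infer that the safety description is biased through the matching. The Protocol does not support this: Descriptive Analyses presents safety outcomes as counts and percentages and does not say that the matched cohort is used. The safety problem that remains is that one index-day event may count on both sides of the baseline boundary.

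This should be fixed before the analytic dataset is built. It is not a reason to doubt the design as a whole.

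**What to change.** Amend the Covariates section and Appendix 2, and carry the rules into the time-point column of Appendix 4:

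- **Index time.** Use the recorded administration time for exposed patients, and assign each matched unexposed patient an index clock time by a stated rule.
- **Pregnancy.** Define it as status known at or before the index time.
- **Vital signs, laboratory results and comedications.** Take the last value before the index time, within the lookback already set.
- **Comorbidities.** Keep the 12-month lookback of Appendix 2 but end it at the index time, so that in-hospital events before transfusion still count. Where a diagnosis carries only a date, state a rule, such as counting it through the day before index.
- **Safety outcomes.** Start the count at the same boundary, so that no event is both covariate and outcome.

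The cost is a few sentences, a timestamp filter, and a few more missing index-day values. A day-before rule for date-only diagnoses would also miss some true pre-transfusion events on the index day.

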**Figure 1. Schematic diagram for retrospective cohort study with risk-set sampling for convalescent plasma exposure**

CP= convalescent plasma

\* Hospital admission includes the earliest encounters at emergency or inpatient departments around COVID-19 confirmation within  $\pm 14$  days.

† The earliest possible date is July 1st, 2020.

Step-by-step risk-set sampling with replacement for the retrospective cohort design to account for confounding and to strategize EHR abstraction at BSWH:

1. Identify patients hospitalized with laboratory-confirmed COVID-19 (Source population)

The study population will be patients with laboratory-confirmed COVID-19 (i.e., RT-PCR test results recorded by the BSWH laboratory informatics systems and/or the EHR system) and received or matched to a patient who received convalescent plasma from July 1st to September 28th. Patients must have at least 28 days of observation opportunity from the date of data pull to the index date (reverse order). Patients cannot have been previously admitted into hospitals due to RT-PCR laboratory confirmed COVID-19.

2. Identify patients who received convalescent plasma (Exposed group)

Blood bank records will be scanned to identify patients who had at least one order to transfuse COVID-19 convalescent plasma using the International Society of Blood Transfusion (ISBT) 128 codes (Appendix 1). The order will be linked to the administration record of the plasma to determine the date and time the product was given.

3. Risk-set sampling and matching variables (Unexposed group)

For each patient who received a first dose of convalescent plasma, we will sample from the source population who did not receive convalescent plasma (Unexposed group) at the same calendar time ( $\pm 2$  days) and match on the following variables. One patient could be sampled at maximum twice; first sampled into the unexposed group and later sampled into the exposed group due to initiation of convalescent plasma transfusion during follow-up.

- Calendar date around the index date within  $\pm 2$  days: Risk-set sampling to match exposed and unexposed patients will account for this factor
- Age ( $\pm 5$  years)
- Sex (female, male)
- Days from hospital admission to the index date

4. Propensity score matching and baseline covariates

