### Sensitivity Analyses

- 1) To assess the COVID-19 cohort definition of hospital admission within ±14 days of laboratory confirmed COVID-19 diagnosis, we will further restrict the source population to those who were admitted into affiliated BSWH hospitals within ±7 days of laboratory confirmed COVID-19 diagnosis. This is because COVID-19 could progress quickly and patients could also transfer to hospitals outside of the network of BSWH with a large time window around COVID-19

confirmation resulting in potential residual confounding by severity and survivor bias by prior treatment

- 2) Instead of ending the observation period at 28 days since the index date, we will continue follow-up until the end of the study period, unless an outcome event occurs earlier. Patients will be followed from the index date until the earliest of the following: 1) death, 2) discharge alive, 3) the end of the study period, or 4) the date of unexposed patients who were administrated COVID-19 convalescent plasma.
- 3) Given that mortality data after hospital discharge is limited and that patients could be discharged for palliative care due to disease worsening, the outcome “discharge alive” will be considered a competing risk for 28-day in-hospital mortality. To account for competing risk of in-hospital death and discharge alive, sub-distribution hazard ratios will be estimated from the Fine-Gray model. Cumulative incidence function will be estimated by modeling the cause-specific hazard function of all causes.

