## V. SAMPLE SIZE

To achieve 80% power for relative risk ratios of at least 0.7 for all-cause mortality, a sample size calculation was performed based on an assumed background survival rate of 0.75 over 28 days among hospitalized COVID-19 patients receiving usual care in the RCT for dexamethasone and a convalescent plasma to comparator ratio of 1:1, 1:2, 1:3 and 1:4. Using a two-sided log-rank test, estimated sample sizes are listed in **Table 1**.

The feasibility assessment found that the maximum number of patients who received convalescent plasma was 729 during April 1, 2020 to August 6, 2020, we greyed out rows in **Table 1** with required sample size surpassing the maximum and deemed those inapplicable.

**Table 1. Sample size estimates given background survival rate of hospitalized COVID-19 patients and 80% of power at a two-sided 0.05 significance level**

Total sample size	Sample size for convalescent plasma	Match ratio	Relative risk ratio
1,000	500	1:1	0.71
1,500	750	1:1	0.76
2,000	1,000	1:1	0.79
2,500	1,250	1:1	0.81
1,000	333	1:2	0.68
1,500	500	1:2	0.74
2,000	666	1:2	0.77
2,500	833	1:2	0.80

Total sample size	Sample size for convalescent plasma	Match ratio	Relative risk ratio
1,000	248	1:3	0.65
1,500	372	1:3	0.71
2,000	496	1:3	0.75
2,500	620	1:3	0.78
1,000	200	1:4	0.61
1,500	300	1:4	0.68
2,000	400	1:4	0.73
2,500	500	1:4	0.76

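### Comfort-care status at index is neither an exclusion nor a covariate, and ICU location and vasopressor use are lesser omissions from the same list

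*Protocol*

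**What the plan says.** In the Protocol, Cohort Sampling step 3 defines the comparator pool: "we will sample from the source population who did not receive convalescent plasma (Unexposed group) at the same calendar time". The matching variables are calendar date (±2 days), age (±5 years), sex and days from admission to the index date. Step 1 requires laboratory-confirmed COVID-19, 28 days of observation opportunity and no earlier COVID-19 admission. Nothing there concerns limits on care.

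Step 4 and Appendix 2 list the propensity-score covariates: age, race and ethnicity, site, comorbidities, named comedications, four vital signs, six laboratory values, and "Disease severity based on level of oxygenation support (Appendix 3) 4-12 hours prior to index". The comedications cover antivirals, hydroxychloroquine, azithromycin, steroids, antiplatelets, IL-6 inhibitors, ACEi/ARB and anti-thrombotics. They do not include vasopressors.

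ICU care appears only as the secondary outcome of ICU transfer. Palliative care appears in Cohort Sampling and in Sensitivity Analyses item 3, each time as something that happens at discharge: "patients could be discharged for palliative care due to disease worsening". The protocol carries its own statistical analysis section and fixes the covariate list itself, so this is a stated choice and not detail left for a later document.

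**The concern.** A comparator should be someone who could have received plasma on the index date and had a similar outlook. A patient already on comfort care only has a very different outlook, and no variable in the list marks that status. If fewer such patients receive plasma (plausible, though the protocol does not say so), they collect among the comparators and raise comparator mortality for reasons unrelated to plasma.

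ICU location and vasopressor use raise a weaker version of the same problem. Within one oxygen category, a non-ventilated ICU patient and a ward patient are distinguished only by vital signs, laboratory values and the other listed covariates. Systolic pressure is in the score, but it can look normal because a vasopressor is running.

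At stake is the primary 28-day in-hospital mortality hazard ratio. The planned check, with absolute standardized differences above 0.1 triggering further adjustment, cannot reveal imbalance in variables that are not on the list.

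**Working it through.** **1. Presence of each factor in the plan**

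| Factor at index | Eligibility | Step 3 matching | Step 4 / Appendix 2 | Partial proxy |
|---|---|---|---|---|
| Comfort-care-only status | no | no | no | none direct |
| ICU location | no | no | no | oxygen category, including invasive ventilation and ECMO |
| Vasopressor use | no | no | no | systolic pressure, heart rate, laboratory values |

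**2. The plan's own design figures**

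Inputs from Section V: "an assumed background survival rate of 0.75 over 28 days", so comparator mortality is 0.25; "To achieve 80% power for relative risk ratios of at least 0.7 for all-cause mortality"; "Using a two-sided log-rank test"; and, from the Table 1 title, "80% of power at a two-sided 0.05 significance level".

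With Freedman's method and the tabulated figure read as a ratio of 28-day death risks (RR), let q be plasma patients per comparator:

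- HR = ln(1 − 0.25·RR) / ln(0.75)
- d = 0.25·n_comparator + 0.25·RR·n_plasma
- z = √(d·q)·(1 − HR)/(1 + q·HR)

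Row with 500 plasma patients at 1:1 and RR 0.71: HR = ln(0.8225)/ln(0.75) = 0.679; d = 125 + 88.75 = 213.75; z = 14.62 × 0.321/1.679 = 2.79; power = Φ(2.79 − 1.96) = 0.80. All 16 rows reproduce to two decimals when solved for the RR giving 80% power. The sample size is therefore not in dispute, and 0.25 and 0.7 are fair reference values.

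**3. Size of a comfort-care imbalance (illustration)**

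Assumptions not in the documents: no true plasma effect; mortality 0.25 in everyone else; an excess fraction f of comfort-care patients among comparators over plasma recipients; in-hospital mortality m in that group; and no reduction of the excess by the rest of the matching.

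Comparator mortality = 0.25(1 − f) + m·f; apparent risk ratio = 0.25 / that value.

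| f | Mortality, m = 0.60 | Risk ratio | Mortality, m = 0.90 | Risk ratio |
|---|---|---|---|---|
| 1% | 0.2535 | 0.99 | 0.2565 | 0.97 |
| 3% | 0.2605 | 0.96 | 0.2695 | 0.93 |
| 5% | 0.2675 | 0.93 | 0.2825 | 0.88 |

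To produce an apparent 0.7 unaided, comparator mortality would have to be 0.25/0.7 = 0.357. The required excess is (0.357 − 0.25)/(m − 0.25), which is 31% at m = 0.60 and 16% at m = 0.90.

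**4. Effect on false positives (illustration)**

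Take the last row of Table 1, 500 plasma patients and 2,000 comparators, the upper limit of "with a match ratio up to 1:4 based on the power calculation". Using a two-proportion test with m = 0.80 and f = 5%:

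- comparator mortality = 0.2375 + 0.04 = 0.2775; difference 0.0275
- pooled risk 0.272; SE under the null = √(0.272 × 0.728 × (1/500 + 1/2000)) = 0.0223
- SE under the alternative = √(0.1875/500 + 0.2005/2000) = 0.0218
- chance of a significant apparent benefit = Φ((0.0275 − 1.96 × 0.0223)/0.0218) = 23%, against a nominal 2.5%

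At f = 2% it is 7%. At f = 5% it runs from 12% (m = 0.60) to 34% (m = 0.95).

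**5. ICU location and vasopressors**

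The documents give neither prevalence nor a direction of selection, so no calculation is offered.

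**The case against.** Four points deserve weight.

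First, a reader might infer that the plan ignores intensity of care altogether. It does not. Appendix 3 separates high-flow and non-invasive support, invasive ventilation and ECMO, and the score also holds vital signs, laboratory values, comorbidities, site and drugs. Secondary Analyses add stratification by ventilator use and by oxygenation if numbers allow. This stands, and it makes ICU location and vasopressor use refinements. It does not supply a marker of comfort care.

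Second, a reader might infer that comfort-care comparators must favour plasma. The primary analysis censors live discharges, so a patient sent to hospice is not counted as a death. The direction therefore depends on most of them dying in hospital, which is why m is varied above. This stands.

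Third, Appendix 3 puts patients with no documented support in the room-air category, so one might infer that patients with support withdrawn are routinely scored as mild. The Covariates section takes the worst oxygenation value 4-12 hours before index, and Appendix 3 sends insufficient flow sheets to clinician review. The misclassification is possible if support ended before that window, but the documents do not show it to be usual.

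Fourth, the Limitations section concedes unmeasured confounding and names quantitative bias analysis, negative outcome controls, E-values and instrumental variables. These are to be considered only if feasible, and none is tied to these variables. The concession is honest but does not close a gap that may be measurable in the same records.

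**Conclusion.** The point holds in a limited form. All three factors are absent from eligibility, matching and the covariate list, and the planned balance check cannot show imbalance in them. Comfort-care status is the substantive omission.

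Under the stated assumptions, an excess of 1% to 5% moves the crude risk ratio from 1 to between 0.99 and 0.88. At the low end that is small beside the design value of 0.7. At the high end it is enough to raise the false-positive rate well above nominal. These figures bound nothing, because prevalence, in-hospital mortality and the absence of any reduction by matching are all assumed. They are also crude risk ratios, whereas the primary estimate is a Cox hazard ratio with discharge censored.

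For ICU location and vasopressor use, neither direction nor size can be determined. The documents do not support a claim that the primary result will be biased by a known amount, or that this imbalance alone could plausibly account for an effect of the size the study seeks.

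**What to change.** - In the analysis cohort, exclude from both groups any patient with an active comfort-care-only order at the index time. If such orders cannot be retrieved reliably, make this a sensitivity analysis and report how complete the field is.
- Add ICU location (yes/no) and vasopressor use, at or before index, to Appendix 2, the propensity score and the balance table. Baseline ICU location would also help define who is at risk for the ICU-transfer outcome.
- Tie the optional bias methods in the Limitations section to any of these variables that cannot be obtained.

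The cost is a few more EHR fields to extract and validate under the procedure in Data Sources, and a small loss of comparators. ICU data are needed for a secondary outcome in any case, although Appendix 4 is still blank, so their availability at index should be confirmed. This is an analytic restriction in a retrospective study and changes no patient's care.
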